The fMRI sub-study will provide refined tests of hypotheses related to cognitive control in a subsample. The Stroop effect is calculated as the difference in reaction time between incongruent and congruent trials. In fMRI data, it is defined as difference in neural activity between incongruent and congruent trials.

1. To evaluate relationships between pre-treatment behavioral and neural measures of cognitive control during the Stroop task and treatment outcome, we will assess the Stroop effect and related neural activity and correlate these indices with treatment outcomes (e.g., longest duration of abstinence, % negative urines).
2. To assess changes in behavioral and neural measures of cognitive control, we will compare indices pre- to post-treatment (e.g., (Incongruent(pre) > congruent (pre)) > (Incongruent(post) > congruent (post))). We will also compare these indices between groups to identify treatment-specific changes.

The MID task allows examination of neural activity during anticipation and receipt of monetary rewards. Anticipation of reward is assessed by comparing neural activity during the reward anticipation phase, and contrasting conditions of \$0 and \$5 (Anticipation of \$5>\$0). Responses to receipt of monetary rewards are assessed by comparing neural activity during the outcome phase (Receipt of \$5>\$0).

1. To examine relationships between pre-treatment behavioral and neural measures of reward processing and treatment outcome, we will assess neural responses during anticipation and receipt of reward (\$5>\$0) and correlate these indices with treatment outcomes (longest duration of abstinence, % negative urines).
2. To evaluate the change in response to monetary rewards from pre- to post- treatment, we will compare indices from this task from pre- to post-treatment (e.g., anticipation of \$5 pre>post, and receipt of \$5 pre>post). We will also compare differences in these indices between groups to identify treatment-specific changes.

For cost and feasibility issues, the fMRI study is limited to patients in groups most likely to show treatment differences, Groups A and C. This design most cost-effectively addresses the issue of if, and how, the availability of monetary based reinforcers alter brain functioning. Based on our earlier work (Devito et al., 2012; Kober et al., 2010) and pilot data, we estimate a medium effect size for changes in regions such as VS and PFC regions. Thirty participants per group is sufficient to determine correlations of  $r \geq .30$  between neural activity in Stroop and MID task and outcome variables. We estimate 25 participants post treatment will be sufficient to assess treatment-related changes in neural activity over time (see Devito et al., 2012).

If effects of reinforcement interventions are moderated by cognitive control, future studies may target these interventions toward patients based on cognitive functioning. As reinforcers add known costs, being able to determine those who will be most positively affected will help direct scarce resources toward patients most likely to benefit. If cognitive function mediates outcomes, future research may refine and test therapies that reduce impulsive choices, and improve cognitive flexibility, inhibition and/or control (Bickel et al., 2011). Combining reinforcement with an intervention that improves cognitive control may result in even more durable effects, which may reduce personal-- and societal—harms related to drug abuse.

**Economic Evaluation.** If primary hypotheses are supported, we will conduct cost-benefit analyses. These interventions can be costly, even when reinforcers are relatively modest. Not only must costs of reinforcers be included, but so must administration costs, which include staff time for managing and delivering reinforcers. Despite costs, these interventions may provide benefits to (1) clinics in terms of enhanced reimbursements (Lott & Jencius, 2009), and (2) society in terms of reductions in healthcare services (hospitalizations, ER visits) and criminal justice system costs, and improvements in workplace productivity (Petry et al., in press c). Using data from the PAC-SAT, this study will determine the net benefit of adding reinforcers, from both clinic and societal perspectives. It will also estimate costs of each week of abstinence attributable to the reinforcement conditions.

- a. Comprehensive administrative costs of interventions will be quantified (Olmstead et al., 2007abc;

Rosenheck et al, 1995; Sindelar et al. 2007ab), including costs of prizes, mileage for purchasing them, and toxicology tests and management (personnel time to arrange testing and reinforcers in both reinforcement conditions, along with costs of cell phone service in the adaptive reinforcement condition only). Costs related exclusively to data collection (arranging for collection and testing of urine samples when it is not reinforced, RA salaries for data collection) will not be included, as they would not be relevant if interventions were applied clinically. Costs for usual clinical services and clinic reimbursement for same will be ascertained.

b. General healthcare costs will be estimated by multiplying service units used per patient by average unit costs. In- and out-patient, day hospital, aftercare and emergency room services will be estimated from CT claims data, and nationally from the Market Scan database, which estimates service costs.

c. Criminal justice (CJ) system costs. Patients receiving reinforcement interventions may have reduced involvement with the CJ system. The PAC-SAT assesses services provided as well as police contacts, court hearings, and incarceration, along with timing of events that resulted in service use so acts occurring before study participation can be separated from those occurring during it in terms of resource utilization. Unit costs of services will be estimated from national reports (Pastore & Maguire, 2003; US Dept. of Justice 2006).

Other societal costs will be obtained on productivity (earnings and workdays affected by drug use) and automobile crashes (including property damage, injuries, and fatalities).

Calculation of net benefits. First, resource utilization and cost data will be used to estimate the average net benefit (i.e., benefits – costs) per patient in each intervention from clinic and societal perspectives (Drummond et al., 2005; Zarkin et al., 2008). Second, average net benefits, and confidence intervals around estimates, will be calculated by subtracting average net benefit of adaptive reinforcement from standard care, or adaptive from traditional reinforcement. Finally, sensitivity analyses (Olmstead et al., 2007a; Drummond et al., 2005) will determine the robustness of the net benefit to alternative assumptions about a variety of cost parameters (e.g., unit costs of services, reimbursements received). If reimbursements rise by maximizing the number of patients attending groups via reinforcement treatment, net benefits are higher as shown by Lott and Jencius (2009).

Cost-effectiveness ratios. If reinforcement engenders net benefits, then it ought to be adopted. However, even in the absence of a net benefit, the incremental cost-effectiveness ratio (ICER) is critical to eventual policy decisions. The ICER is calculated as: (i) incremental costs to (ii) incremental effectiveness (difference between average effectiveness of treatments in terms of weeks of abstinence). Using expert panel recommendations (Gold, 1996; Johanneson, 1996; Weinstein, 1996), we will present traditional ICERs and uncertainty of the ratios (Gold, 1996; O'Brien et al., 1994) and derive a single synthetic measure of multiple indicators of effectiveness, including quality of life (Hargreaves et al., 1997; Rosenheck et al., 1998). We will also conduct acceptability curve analysis to provide policy relevant interpretations (Fenwick et al, 2001,2004; Lothgren & Zethraeus, 2000; Polsky et al., 1997; vanHout et al., 1994). Multiple samples are selected randomly (bootstrapped), with replacement, from the original sample to approximate the larger population. These analyses can also be performed with important subsamples, such as patients with greater sensitivity to rewards if this is determined to be an important predictor of response to reinforcement interventions. Incremental cost and effectiveness values and ICERs can be calculated for each new sample and compared with theoretical "willingness to pay" values for an outcome, such as days abstinent. Such analyses inform policy makers in decision-making (Olmstead et al, 2007ab; Sindelar et al, 2007b) and can be conducted with samples even smaller than those herein (Olmstead et al., 2007c,2009; Sindelar et al., 2007a).

In sum, this study allows for rigorous determination of costs and benefits of interventions that accrue to clinics and society. A clinic perspective is crucial because, at least in the immediate future, agencies are unlikely to fund expanded services unless they are cost beneficial. Societal perspectives (ICER analyses) are critical for future policy that might allocate state and federal funding to further support reinforcement interventions, as is now being done on a limited basis for substance abuse care as well as in some other health care arenas. Only a comprehensive study such as this can address multiple perspectives, ranging from individual differences in cognitive response to treatments, to clinical and societal effects. The ultimate goal of this proposal, which integrates these perspectives, is to optimize benefits of reinforcement interventions and extend them to the patients most likely to derive clinically significant, and durable, reductions in drug use.

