This adaptive intervention is expected to increase the proportion of patients who receive large or full "doses" of reinforcement therapy. Less than half of patients in reinforcement interventions complete intended durations of care, even when they are only 12 weeks (Petry et al., 2004,2005ab,2006a,2011a,2012ab). In part, attrition from reinforcement interventions mimics discontinuation from standard care. Although reinforcement interventions enhance participation in clinical care relative to non-reinforcement treatments (Petry et al., 2005ab,2006,2011a,2012ab), patients stop providing samples and no longer receive reinforcers for abstinence once they cease attending groups. By encouraging patients who no longer attend group therapy to continue earning reinforcers for abstinence on their own self-selected and relatively minimal schedule, this progressive VI reinforcement intervention is likely to engage patients for longer durations. If efficacious, a VI schedule that adjusts to patient progress has the potential to change the course of how reinforcement interventions are implemented.

**3. Cell phone technology** will maintain contact with patients and inform them of testing schedules. Cell phones are increasingly applied in the context of health behaviors, and this study will use a novel approach to integrate cell phones into reinforcement interventions. Patients will receive unlimited cell service, highly desired because most patients with free plans use up allotted monthly minutes quickly. According to procedures worked out in prior trials (see prelim studies), patients will maintain use of study cell phones so long as they submit samples when contacted and asked to do so, regardless of results of the samples. This technology also provides a means by which staff can prompt sample submission and assess the natural course of relapse, and how it is impacted by reinforcement interventions, using objective indices even after patients cease attending treatment.

**4. Neurocognitive assessment.** This study is also novel in that it will evaluate neural processes underlying cognitive control and reward processing in the context of reinforcement interventions. Many neurobiological

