- State-Trait Anxiety Inventory (STAI) is a widely used measure of both consistent and transient stress and anxiety (Kendell et al., 1976) and is included as a potential moderator of treatment effects.
- Quality of Life Inventory (QOL; Frisch et al., 1992) assesses satisfaction with and importance of life areas (work, health, recreation, etc) and is positively impacted by reinforcement interventions (Petry et al., 2007b).
- HIV Risk Behavior Scale (HRBS; Darke et al., 1991) measures injection and sexual risk behaviors reliably and validly (Petry, 2001b), which decrease in reinforcement interventions (Hanson et al, 2008; Petry, et al., 2010a, 2011a). Non-overlapping items on the Risk Assessment Battery (Navaline et al., 1994) will be included. The HRBS will assess lifetime at baseline, past month at the Month 1 interview and the past 3 months at all other timepoints, including baseline.
- The Risk Assessment Battery (RAB; Navaline et al., 1994) is a comprehensive assessment of risk behaviors (e.g., Chaudhury et al., 2010; Disney et al., 2006; Takizawa et al., 2007; Tourian et al., 1997). Questions from the RAB (that do not overlap with the HRBS) will assess lifetime and past 3 months at baseline, the past month at the Month 1 interview and the past 3 months at all other timepoints.

- The Service Utilization Form (SU; Olmstead et al., 2007) will be used to evaluate services received and costs. An abbreviated version will be administered at follow-up.
- The Timeline Follow-back (TLFB; Sobell et al., 1980) uses calendar prompts to elicit specific information about the frequency and intensity of substance use over time intervals with good test-retest reliability and validity (Sobell & Sobell, 1992). It will assess days and quantity of alcohol use and days of cocaine, amphetamine, methamphetamine, opioid, benzodiazepine, marijuana or other drug use 3 months before treatment, throughout treatment, and since the last interview at follow-up.

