During the COVID-19 outbreak and until exposure risks to participants and research assistants are reduced, study visits will be completed over the phone. Participants who complete follow-up visits over the phone will miss some components (i.e. sample submission) but will receive the full \$50 follow-up payment. If the interval between the remote follow-up and opportunity to collect samples/measures is minimal, participants may be able to submit these missed components after risk decreases. Payments for completed mailed packets will remain \$30.

**Incarceration:** This is a minimal risk study that recruits non-prisoner patients from substance abuse treatment programs. However, a portion of the study patients are likely to be incarcerated during the study period due to illegal activities that are common in this population. If a patient is incarcerated during study participation, all study procedures are suspended except the evaluations. In the ICF, patients indicate whether or not they would like the evaluation questionnaires sent to them in prison. The mailing delivered to the incarcerated patient only contains the evaluation questionnaires and a cover letter indicating the questionnaires are follow-up to a study the patient participated in at the University of Connecticut Health Center. A stamped and addressed return envelope is also provided with the questionnaires. If the patient completes and returns the questionnaires for Month 1, 3, 6, 9, 12, 15 or 18, they will receive \$30 in the form of a check. The patient will receive the check after their release from incarceration or they may designate a person to whom the check should be sent during their incarceration. The patient is notified in the ICF that their participation in this study while incarcerated will have no effect on their eligibility for parole.

**Randomization:** Patients will be randomly assigned to one of the three conditions. An urn randomization program (Stout et al., 1994), will balance patients based upon baseline sample results (cocaine positive or negative) and whether or not they were in a controlled environment in the past month (e.g. jail, inpatient detoxification). These variables are used because initial toxicology results are a strong predictor of outcomes (Petry et al., 2004; Preston et al., 1998; Stitzer et al., 2007), and controlled environments impact drug use. A separate 'urn' will be employed in each clinic, thereby stratifying on clinic as well.

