Although some patients have their own cell phones, >90% of those with phones have pre-paid or government-limited plans, resulting in highly unreliable service (most quickly use up all their minutes). In an informal survey, 93% stated that patients would submit samples up to twice weekly for 6 months in exchange for unlimited cell service. Patients who prefer to use their own cell may elect to receive a \$25 gift card for each month during which they do not miss more than one randomly selected test day in a row. (Patients with their own phones may switch to study phones at any time to ensure contact). If a study phone is turned off, it will be reinstated as soon as the patient submits a sample (i.e., the patient comes to the clinic or UCHC to submit a sample on their own, without being prompted to do so). After discontinuation of cell service, patients will be informed in writing about how to reinstate it. Once cell service is reinstated, similar rules related to continued use will be applied (and service discontinued if they miss >1 prompted test day in a row).

As in all our studies, research will be separate from clinical care. The clinics rarely test for drug use, and only upon suspicion. Clinic-requested samples will occur separately from research samples, and results not shared, as arranged previously (Petry et al., 2011a, 2012a). RAs will congratulate patients for each drug for which they test negative, and if positive, encourage them to discuss any use in group (Human Subjects).

We expect that most patients will not continue in treatment at the clinics for 24 weeks, and median length of stay is <5 weeks. Although prompting sample submission via cell phones will increase sample submission, we expect any effect related to enhancing clinic group attendance will be modest. For >15 years, patients in our studies have been returning to clinics for study procedures (sample submission, follow-ups),

which are clearly differentiated from treatment procedures. Even if these procedures do enhance clinical services received, the effects will be similar across groups as all receive the same incentives for sample submission (i.e., cell service).

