**Data Analysis.** An important issue preceding analyses is to identify baseline differences between groups despite random assignment. Differences between groups that may be related to outcome (e.g., psychiatric diagnoses, dependence severity, clinic services received) will be used as covariates or fixed factors, as appropriate. Analysis will be conducted on an intent-to-treat basis, using all randomized patients, and both short-term (changes from baseline to month 6) and longer-term (throughout the 18-month follow-up) efficacy will be evaluated. The primary outcome is longest duration of cocaine abstinence, a continuous variable that can be transformed if needed. Groups will be compared using t-tests for normally distributed data, or ANCOVA if covariates are included. The design includes 3 treatment groups, allowing for analyses of two main effects.

Primary aim # 1 is to examine the efficacy of adaptive progressive VI reinforcement. We will compare those randomized to Group C vs Group A with respect to longest duration of abstinence during the 24-week intervention period and throughout the 18-month follow-up period.

Primary aim #2 is to assess if adaptive reinforcement improves duration of abstinence achieved relative to traditional reinforcement. We will compare those randomized to the two reinforcement conditions with respect to during treatment and long-term abstinence outcomes.

Secondary aims are to evaluate the impact of the interventions on other indices of stimulant and secondary drug use outcomes. Using the same contrasts above, we will compare groups with respect to: proportions of submitted and expected samples that test negative for stimulants and other drugs (alcohol, opioids, THC), and subjective reports of use (SUC % abstinent days). The first rely on objective indicators and such data will be available from all randomized patients. Subjective reports will supplement objective indices, and patients can be considered using if either index is positive. In terms of proportional data, missing samples will be considered missing (not impacting the denominator) in one analysis, and positive in another to consider the range of possibilities with respect to drug use outcomes. Because Group B has more expected samples (48) than the other groups ( $\geq 18$ ), proportional data for expected samples will rely upon the cell phone prompted samples ( $\geq 18$ ), designed to be similar across conditions, to conservatively test group differences.

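### The primary model is chosen from observed group differences and defaults to an unadjusted t-test, so the three factors used to balance randomisation would rarely be adjusted for and power is lost

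*Combined protocol and SAP*

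**What the plan says.** The Data Analysis paragraph opens with "An important issue preceding analyses is to identify baseline differences between groups despite random assignment". It continues: "Differences between groups that may be related to outcome (e.g., psychiatric diagnoses, dependence severity, clinic services received) will be used as covariates or fixed factors". The test follows from that step: "Groups will be compared using t-tests for normally distributed data, or ANCOVA if covariates are included". There is no list of covariates for the primary outcome, no threshold for calling groups different, and no adjustment that applies regardless of the data.

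The Randomization paragraph describes an urn scheme that balances on the baseline cocaine sample result and on a controlled environment in the past month, and gives a reason: "These variables are used because initial toxicology results are a strong predictor of outcomes". It adds: "A separate 'urn' will be employed in each clinic, thereby stratifying on clinic as well".

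Site and baseline positive samples do appear as regressors later in Data Analysis, where predictors of outcome are discussed. That is an exploratory regression, and its list also contains days of group attendance, which accrue after randomisation. It is not the comparison that tests either primary aim.

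**The concern.** Two things look wrong.

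First, the primary model depends on the data. Seeing a group difference is the only route by which the plan says a covariate enters. The three factors the sponsor chose to balance on, one of which it calls strongly prognostic, are the ones least likely to show a difference. Balancing on a prognostic factor and then leaving it out makes the reported standard error larger than the true sampling variability of the treatment difference. Type I error falls below 0.05, and power falls in both primary comparisons.

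Second, the timing of the services covariate is unclear. The lead-in about baseline differences, and a baseline column for service use and clinic attendance in the assessment schedule, allow a baseline reading. Four facts point the other way:

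- Consent is sought within 7 business days of clinic admission, so little care at the study clinic precedes randomisation.
- The Service Utilization Form, which "will be used to evaluate services received and costs", is repeated through month 18.
- The standard-treatment section uses nearly the same phrase for care received during the study: "Even if these procedures do enhance clinical services received, the effects will be similar across groups".
- Innovation item 2 states that "reinforcement interventions enhance participation in clinical care relative to non-reinforcement treatments".

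Adjusting for in-study services could therefore remove part of the C versus A effect. For C versus B both arms are reinforced, the documents establish no direction, and no bias is claimed.

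**Working it through.** **Inputs.** From the power analysis: d = 0.46 for Aim 1, d = 0.35 for Aim 2, alpha 0.05 with sidedness not stated, target power 0.80, allocation 60:110:110 (A:B:C). From Methods: six named clinics. Assumed, because the documents give no figure: the joint R-squared of the three randomisation factors.

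**Step 1. The plan's own figures.** Power comes from the noncentral t distribution with noncentrality d × √(n₁n₂/(n₁+n₂)) and n₁+n₂−2 degrees of freedom.

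- Aim 1, 60 v 110: √(6600/170) = 6.231; 0.46 × 6.231 = 2.866; df 168. Two-sided power is **0.813**. With 60 v 60 it is 0.705 two-sided and 0.805 one-sided. So 60 reproduces one-sided, or two-sided at the actual unequal allocation.
- Aim 2, 110 v 110: √55 = 7.416; 0.35 × 7.416 = 2.596; df 218. Power is **0.734** two-sided and 0.827 one-sided. By the t-test, 80% power needs 130 per group two-sided or 102 one-sided, so 110 reproduces under neither.

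**Step 2. Always adjusting.** Replace d by d/√(1−R²) and take 7 further degrees of freedom (1 + 1 + 5 for six clinics). The last column is the type I error of the unadjusted test if balance were perfect: 2 × [1 − Φ(1.96/√(1−R²))].

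| R² (assumed) | Aim 1 power | Aim 2 power | Aim 2, one-sided | Type I, unadjusted |
|---|---|---|---|---|
| 0 (no adjustment) | 0.813 | 0.734 | 0.827 | 0.050 |
| 0.05 | 0.832 | 0.755 | 0.844 | 0.044 |
| 0.10 | 0.852 | 0.777 | 0.860 | 0.039 |
| 0.15 | 0.871 | 0.800 | 0.877 | 0.034 |
| 0.20 | 0.890 | 0.824 | 0.894 | 0.028 |
| 0.25 | 0.908 | 0.847 | 0.910 | 0.024 |

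The seven degrees of freedom cost 0.001 or less in power.

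**Step 3. How often the stated rule would admit a randomisation factor.** The plan gives neither a threshold nor urn settings, so this was simulated, reading a difference as p < 0.05 and making only the three randomisation factors eligible.

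- Separate urns in six clinics, 30% cocaine positive, 35% controlled environment, R² of 0.10 and 0.25 split 70/15/15 over toxicology, environment and clinic, 4,000 trials per setting: any factor is admitted in 1.8–2.5% of trials for C v B and 4.6–5.1% for C v A. Power under the rule is 0.74 (Aim 2) and 0.81 (Aim 1), against 0.77–0.83 and 0.84–0.89 when always adjusted. Type I error under the rule is 0.034–0.047. Monte Carlo error is about 0.007 on power and 0.003 on type I error.
- A biased-coin approximation that may balance more tightly than the real program, with 30% and 40% prevalence, 2,000 trials per setting: no factor was ever admitted. At R² = 0.20, power under the rule against pre-specified adjustment was 0.839 v 0.893 (Aim 1) and 0.765 v 0.838 (Aim 2). Type I error was about 0.031 against 0.047–0.049. The mean reported standard error was 0.160 v 0.144 and 0.135 v 0.121.

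**Step 4. In-study services, C v A, only if they were adjusted for.** Let treatment shift services by a SD and let the outcome slope on services be b (both assumed). The amount removed is a × b, and the power calculation uses (0.46 − ab)/√(1−b²) at 60 v 110 with one degree of freedom lost.

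| a, b | Removed (SD) | Share of 0.46 | Aim 1 power |
|---|---|---|---|
| 0.1, 0.2 | 0.02 | 4% | 0.794 |
| 0.2, 0.3 | 0.06 | 13% | 0.738 |
| 0.4, 0.5 | 0.20 | 43% | 0.460 |
| 0.1, 0.5 | 0.05 | 11% | 0.835 |

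The last row shows that power need not fall, although the estimate is still shifted.

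**The case against.** The strongest reply is that the harm is modest and its size is assumed. A strong predictor is not a number. At R² = 0.05 the gain is only about two points in each aim, and Aim 1 already exceeds 0.80 unadjusted. The omission makes the test conservative, and no inflation of type I error is shown. The two-sided Aim 2 shortfall against 0.80 is mainly a matter of sample size and sidedness. All of that stands, and it limits the size of the point. It does not supply a reason to prefer the stated rule.

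The plan also does not forbid including the randomisation factors, and an analyst using judgement might add them. That is true, but the only route the text gives is an observed difference, so their inclusion is not pre-specified. The admission rates depend on an assumed p < 0.05 trigger and assumed urn settings. The simulated rule is also narrower than the plan's, since psychiatric diagnoses or dependence severity could be admitted too. The percentages are illustrative; both simulations nevertheless support rare admission under that trigger.

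On services, the sentence most naturally refers back to baseline differences, and baseline values are collected. That reading may well be what was meant. This part is therefore a request to state the measurement time, and the shifts and slopes in step 4 should carry no weight in judging importance.

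**Conclusion.** The concern holds. The primary comparison has no pre-specified covariates, and the stated rule tends to exclude the factors the trial balances on.

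- **Direction:** the loss follows from the design. Omitting balanced prognostic factors widens the standard error and makes the test conservative.
- **Size:** this rests on an assumed R². At 0.10–0.25 the nominal gain from always adjusting is about 4 to 10 points of two-sided power for Aim 1 and 4 to 11 for Aim 2, taking d = 0.46 and 0.35 as being in unadjusted SD units. Against the simulated rule at the same R² values, the gain is about 3 to 8 and 3 to 9 points.
- **Confidence:** high for the missing pre-specification, lower for any particular power figure.

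The services wording is an ambiguity to be cleared up, and the conclusion does not depend on it. The point is worth acting on because the better method costs almost nothing; it does not threaten the validity of the primary test.

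**What to change.** In Data Analysis, define the primary model for both aims, and for both the 24-week and 18-month windows, as ANCOVA of longest duration of abstinence on treatment, baseline cocaine result (positive or negative), past-month controlled environment (yes or no) and clinic, fitted whatever the observed balance. Delete the step that selects covariates from group differences. If other baseline covariates are wanted, name them before group data are seen. State that every covariate in the primary comparisons is measured before randomisation, and say so explicitly for services received. Keep in-study services and attendance for descriptive or mediation analyses. The predictor regressions can stay as exploratory, with a note that they do not estimate the treatment effect.

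The cost is analysis wording only: no new data, no extra patients, and seven covariate terms whose cost in power is 0.001 or less.
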